1. INTRODUCTION

1.1 Background

Remote Ischemic Preconditioning in PCI

Even though technical advances in percutaneous coronary intervention (PCI), over the past two decades, have resulted in a safe procedure with minimal complications, in several patients the procedure is complicated by peri-procedural injury, detected by elevated values of biomarkers of myocardial necrosis. According to the biomarker used, the incidence of peri-procedural myocardial injury in elective procedures ranges between 20% and 45%, with widespread adoption of troponin tests allowing detection of smaller amounts of necrosis.^{1,2} Peri-procedural cardiac troponin elevation has been associated with new irreversible myocardial injury, detected by delayed-enhancement magnetic resonance imaging,³ and even though the prognostic significance of peri-procedural CK-MB and cardiac troponin elevation has been highly debated, several studies have reported that peri-procedural injury is associated with worst prognosis.^{4,5}

Peri-procedural myocardial injury may be categorized according to its pathogenesis into two types.² Type 1 or proximal type of peri-procedural myocardial injury is mainly attributed to side branch occlusion during balloon inflation or stent deployment. Side branch occlusion, occurring in 12.5-19% of cases, is mainly caused by plaque shift, thrombus formation, or dissection at the takeoff of the side branch. Type 2 or distal type of peri-procedural myocardial injury, which accounts for 50-75% of all cases, results from distal embolism of atheromatous material, platelet activation and thrombosis precipitating microvascular plugging, neurohormonal activation and modulation of vascular and myocardial functions, and oxidative stress with inflammation.

If peri-procedural injury incidence could be attenuated, then clinical outcomes of stable CAD following PCI may be expected to improve. One approach to reducing myocardial injury is through cardioprotective intervention.² Conditioning the myocardium to protect against procedural ischemia/ reperfusion (I/R) injury is such an intervention used in both the experimental and clinical setting.⁶ Conditioning refers to an intrinsic myocardial mechanism of cardioprotection triggered by inducing brief, sub-lethal episodes of ischemia and reperfusion.⁶ Conditioning can be defined according to the temporal relationship between the conditioning intervention and onset of the ischemic insult - conditioning before the sustained insult is preconditioning, conditioning during the sustained insult is perconditioning, whilst conditioning after the sustained insult is postconditioning.⁷ Furthermore, preconditioning of the myocardium can be achieved from a remote organ, via a non-invasive approach.⁷ Here, focus is on remote ischemic preconditioning (RIPC) and its potential effect to reduce myocardial I/R injury induced during PCI, thus improving clinical outcomes of elective PCI.

Mechanism of preconditioning and the role of adenosine

The mechanism behind the protective effects of RIPC in the setting of PCI has been recently reviewed by our group.⁸ Mechanistically, preconditioning is best considered in terms of triggers, mediators, and effectors.^{6,9} The activators of the preconditioning cascade are termed “triggers” and are broadly extracellular receptor/ligand interactions with autocrine, endocrine or paracrine signaling molecules. The ischemic conditioning signal is a summation of signals

derived from multiple disparate receptor/ligand interactions, which reaches a threshold once sufficient combined signals are generated.^{6,9}

Among the most well-established preconditioning triggers, are adenosine, bradykinin and opioids. Adenosine is thought to be crucial in initiating the preconditioning cascade.¹⁰ Activation of the G-coupled adenosine A1 receptor triggers IPC protection, whereas adenosine receptor antagonists can block IPC protection.¹¹ In a similar manner, bradykinin infusion induces cardioprotection which can be abolished by bradykinin receptor blockers.¹²

Adenosine is a purine nucleoside produced primarily through the metabolism of ADP, and its plasma levels increase after cellular stresses such as injury, ischemia/reperfusion, or inflammation.¹³ Adenosine is rapidly taken up by cells through sodium-independent equilibrative nucleoside transporters (ENT 1/2) and sodium-dependent concentrative nucleoside transporters (CNT 2/3).¹⁴

Intracellular adenosine is metabolized to inosine by adenosine deaminase or transformed into adenine nucleotides by adenosine kinase.¹⁵ Because of its rapid cellular uptake and metabolism, extracellular adenosine has a half-life of a few seconds, which can be prolonged by inhibition of its transport into cells.¹⁶

Several studies provide evidence that ticagrelor inhibits cellular uptake of adenosine.^{14, 17, 18} Ticagrelor inhibited adenosine uptake by washed human erythrocytes and by human, dog, and rat cell lines. Considering that the experiments were performed under sodium-free conditions and with cell lines that express ENT1 but not ENT2, it was assumed that ticagrelor inhibits sodium-independent ENT1.¹⁷ The identity of the target transporter was recently confirmed with cells transfected with human transporters (ENT1, ENT2, CNT2, and CNT3). In these experiments, ticagrelor significantly inhibited adenosine uptake only in cells that expressed ENT1.¹⁴

1.2 Research hypothesis

We will study the effect of ticagrelor on the reduction of PMI and the incidence of post-PCI MI with the use of RIPC. Our primary research hypothesis is that treatment with ticagrelor will potentiate the effects of RIPC and, therefore, reduce PMI, as assessed by post-procedural troponin release.

1.3 Rationale for conducting this study

Our research group has significant experience in utilizing RIPC for the prevention of periprocedural myocardial injury (PMI) in the setting of PCI.⁸ We have recently demonstrated in a randomized clinical trial that RIPC can effectively reduce PMI and post-PCI myocardial infarction in the setting of ad hoc PCI for stable coronary artery disease.¹⁹ Furthermore, we have recently published a meta-analysis, providing compelling evidence for the beneficial effects of RIPC in the setting of elective PCI.²⁰

In this setting we have designed a randomized clinical trial to assess the effect of ticagrelor on the reduction of PMI and the incidence of post-PCI MI with the use of RIPC.

1.4 Benefit/risk and ethical assessment

Peri-procedural cardiac troponin elevation has been associated with new irreversible myocardial injury and several studies have reported that peri-procedural injury is associated with worst prognosis. According to the available evidence, the prognostic significance of PMI is more pronounced when pre-procedural troponin is increased, i.e. in the setting of acute coronary syndromes. Data from the Cardiac Remote Ischemic Preconditioning in Coronary Stenting (CRISP Stent) study support that implementation of a RIPC protocol during PCI may reduce major adverse cardiovascular events during long-term follow-up and that post-procedural troponin I concentration associated with the development of major adverse cardiovascular events.²¹ If this protective effect is potentiated with treatment with ticagrelor, patients are expected to further benefit.

Ticagrelor has been shown to reduce significantly the rate of death from vascular causes, myocardial infarction, or stroke in patients with an acute coronary syndrome (ACS) with or without ST-segment elevation, compared to clopidogrel. These benefits were obtained without an increase in the rate of overall major bleeding but with an increase in the rate of non-procedure-related bleeding.²² Accordingly, treatment with ticagrelor in patients undergoing PCI for non ST-segment elevation ACS (NSTEMI-ACS) or ST-segment elevation MI (STEMI) has been approved by the European Medicines Agency (EMA) and carries a Class I level of evidence B recommendation from the European Society of Cardiology (ESC)²³

Even though ticagrelor has not received approval in patients with stable CAD, several clinical trials have assessed its pharmacodynamic and pharmacokinetic effects in comparison with clopidogrel in this patient population, proving superior efficacy in platelet inhibition with a safety profile consistent with previous studies.^{24,25,26,27}

In treating patients with stable CAD with a more potent antiplatelet drug, lies a risk of increased bleeding, even though according to previous studies this is expected to be minor and non-life threatening (PLATO).²² To minimize patient risk, patients with a CRUSADE [Can Rapid risk stratification of Unstable angina patients Suppress ADverse outcomes with Early implementation of the ACC/AHA guidelines] bleeding risk score >50 will be excluded from the study. Furthermore, duration of ticagrelor treatment will be kept minimal (1 month). Furthermore, since use of ticagrelor is not recommended as part of initial triple anticoagulation therapy, patients with an indication for oral anticoagulation will also be excluded.

Finally, even though all efficacy endpoints of the present study are to be evaluated at 24 hours following PCI, it is considered in the subjects' interest to continue study treatment for a period of a month, during which period all enrolled subjects will be monitored for the safety endpoint and other adverse events. This is a result of a lack of available evidence to support switching from a more potent to a less potent antiplatelet drug within 24 hours of PCI, and a paucity of studies regarding the optimal clopidogrel loading dose when switching from ticagrelor to clopidogrel.²⁷ Furthermore, receiving a loading dose of ticagrelor and within 24 hours a loading dose of clopidogrel combined with peri-procedural anticoagulation, may significantly increase bleeding risk.

2. STUDY OBJECTIVES

2.1 Primary objective

The primary objective of this study is to demonstrate superior efficacy of a combination of ticagrelor and RIPC in the reduction of PMI compared to a clopidogrel-RIPC combination or ticagrelor alone, by evaluating post-procedural cardiac Troponin I (cTnI) levels, defined as cTnI at 24 hours post-PCI.

2.2 Secondary objectives

Evaluation of chest pain during coronary balloon occlusion. Chest pain severity assessed with a numerical 10 point scale (0: no pain, 10: most severe discomfort ever experienced)

Evaluation of ECG evidence of ischemia during coronary balloon occlusion. ST-segment deviation as monitored during coronary balloon occlusion.

2.3 Safety objective

Safety monitoring will be performed daily during the index hospitalization. The presence of adverse events will be assessed by history, detailed physical examination and appropriate laboratory tests that will be described in the protocol accordingly.

In addition patients will be instructed to contact the study personnel in case of any emergency situation whereas an adverse event reporting system will be available throughout the study.

In detail, bleeding according to the Thrombolysis in Myocardial Infarction (TIMI) bleeding criteria will be recorded and assessed throughout study duration. According to these criteria bleeding is defined as follows:

Non-CABG Related Bleeding:

1. Major

- Any intracranial bleeding (excluding microhemorrhages <10 mm evident only on gradient-echo MRI)
- Clinically overt signs of hemorrhage associated with a drop in hemoglobin of ≥ 5 g/dL or a $\geq 15\%$ absolute decrease in haematocrit
- Fatal bleeding (bleeding that directly results in death within 7 d)

2. Minor

- Clinically overt (including imaging), resulting in hemoglobin drop of 3 to <5 g/dL or $\geq 10\%$ decrease in haematocrit
- No observed blood loss: ≥ 4 g/dL decrease in the haemoglobin concentration or $\geq 12\%$ decrease in haematocrit

- Any overt sign of hemorrhage that meets one of the following criteria and does not meet criteria for a major or minor bleeding event, as defined above
- Requiring intervention (medical practitioner-guided medical or surgical treatment to stop or treat bleeding, including temporarily or permanently discontinuing or changing the dose of a medication or study drug)
- Leading to or prolonging hospitalization
- Prompting evaluation (leading to an unscheduled visit to a healthcare professional and diagnostic testing, either laboratory or imaging)

3. Minimal

- Any overt bleeding event that does not meet the criteria above
- Any clinically overt sign of haemorrhage (including imaging) associated with a <3 g/dL decrease in haemoglobin concentration or <9% decrease in haematocrit

Bleeding in the Setting of CABG:

- Fatal bleeding (bleeding that directly results in death)
- Perioperative intracranial bleeding
- Reoperation after closure of the sternotomy incision for the purpose of controlling bleeding
- Transfusion of ≥ 5 U PRBCs or whole blood within a 48-h period; cell saver transfusion will not be counted in calculations of blood products.
- Chest tube output >2 L within a 24-h period

3. STUDY PLAN AND PROCEDURES

3.1 Overall study design and flow chart

The TRIP study will be a randomized, assessor-blind, active comparator-controlled, clinical trial using a 2×2 factorial design, with 1:1 patient allocation to ticagrelor or clopidogrel and within each treatment a 1:1 allocation to RIPC or control.

According to the study plan, patients who are referred for coronary angiography or NSTEMI-ACS may be screened for randomization.

	Day 1/ Screening	Day 2	Day 3	Day 30 (±5days)
Informed consent form	x			
Inclusion criteria	x			
Exclusion criteria	x	x	x	

Medical history	X			X
Concomitant disease	X			X
Concomitant medication	X	X	X	X
Physical examination (vital signs)	X	X	X	X
ECG	X	X		
Local laboratory values	X	X	X	
Randomization	X	X		
Treatment initiation	X			
RIPC		X		
Coronary angiography assessment		X		
PCI		X		

[figure not shown]
Day 1 of the study is defined as the day of randomization to ticagrelor versus clopidogrel. This should be chosen by the investigator to be the day before the scheduled PCI procedure.

Day 2 of the study is defined as the day of randomization to RIPC or control and subsequent (within 1 hour) coronary angiography and PCI.

In patients already treated with clopidogrel for 3 to 7 days, actions performed on Day 1 and Day 2 may be combined into a single day provided that;

- a. Twenty four hours have elapsed between the last dose of clopidogrel and the randomization to the ticagrelor or clopidogrel group, and
- b. There is sufficient time (2-4 hours) between the randomization and subsequent intake of clopidogrel or ticagrelor and the 2nd randomization to the RIPC or control group.

If for unforeseen reasons, PCI is not conducted within the prespecified timeframe the patient should be withdrawn from the study.

* In case of a patient already on clopidogrel for 3-7 days, ticagrelor loading dose is administered on the day of the procedure (24 hours after the last clopidogrel dose), and no 2nd ticagrelor dose is administered. ** In case of a patient already on clopidogrel for 3-7 days, no loading dose of clopidogrel is administered, but the patient ideally receives 75mg clopidogrel 2-3 hours before the procedure.

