5.1.1 Procedures for randomization

The TRIP study will be a randomized, assessor-blind, active comparator-controlled, clinical trial using a 2×2 factorial design, with 1:1 patient allocation to ticagrelor or clopidogrel and within each treatment a 1:1 allocation to RIPC or control. Patient randomization in the ticagrelor and the clopidogrel group will take place using sealed, opaque envelopes containing a computer-generated randomization scheme. Using a similar procedure, patients will be randomly assigned to RIPC or no RIPC within 1 hour before the procedure.

5.2 Procedures for handling subjects incorrectly enrolled or randomized or initiated on investigational product

Subjects who fail to meet the inclusion and exclusion criteria are defined as screening failures. The investigator will maintain a Screening Log which includes screen failures. The log will document the subject number, subject initials, demographics and the reason(s) for excluding the patient from the study. This log will be kept in the Investigator's Study File. It will be used to determine systematic bias in selection of patients for entry into the study.

Subjects who withdraw or are withdrawn from the study following randomization, before investigational product initiation should:

- Have the reason(s) for their withdrawal recorded

Subjects who withdraw or are withdrawn from the study following randomization and investigational product initiation should:

- Have the reason(s) for their withdrawal recorded
- Be asked about the presence of any AEs and if so should be followed up by regular scheduled visits, telephone contact, correspondence or home visits until satisfactory clinical resolution of AEs is achieved.
- Be seen by an investigator and all final assessments will be performed and recorded in the termination page of CRF.
- Have at least one follow-up contact for safety evaluation during the 30 days following the last dose of study treatment.
- In the event of pregnancy, the subject should be monitored until conclusion of the pregnancy and the outcome of pregnancy reported.
- Have study treatment returned (according to accountability practices)

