12.2 Methods of statistical analyses

The efficacy analysis will be performed in the population of subjects valid for safety analysis.

The statistical assessment of the primary outcome measure (post-procedural cTnI) will be performed using ANCOVA (analysis of covariance), with post-procedural cTnI as a dependent variable, -ticagrelor/clopidogrel treatment and –RIPC/no RIPC as fixed factors and pre-procedural cTnI as a covariate. If not mentioned otherwise, all statistical tests will be performed tow-sided with a type I error rate of 5% and 95% confidence intervals (two-sided) will be given.

The statistical assessment of the secondary outcome measures (pain score, and ST-segment deviation) will be performed using ANOVA (analysis of variance). The ANOVA tests the null hypothesis that samples in two or more groups are drawn from populations with the same mean values. If the ANOVA test is statistically significant, pairwise comparison of subgroups will be performed with the Tukey-Kramer test. If not mentioned otherwise, all statistical tests will be performed tow-sided with a type I error rate of 5% and 95% confidence intervals (two-sided) will be given.

The safety analysis will be performed in the population of subjects valid for safety analysis.

The incidence of the composite of major and non-major bleeding according to the TIMI criteria and the incidence of major bleeding will be tabulated and further analyzed using Fisher's exact test. Fisher's exact test is a significance test for a 2x2 table. This test evaluates all distribution probabilities for a 2 x 2 table and produces an exact probability for a given set of observed frequencies. The null hypothesis is that the row and column variables are unrelated, or that there is no difference in the respective proportions. If not mentioned otherwise, all statistical tests will be performed two-sided with a type I error rate of 5% and 95% confidence intervals (two-sided) will be given.

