12.3 Determination of sample size

According to our previous research¹⁹ and other available studies on the subject²⁰ we have assumed post-procedural cTnI to be approximately 0.10ng/mL in the RPC group (0.08ng/mL for the ticagrelor group and 0.12 for the clopidogrel group) and approximately 0.19ng/mL for the control group (0.14ng/mL for the ticagrelor group and 0.24 for the clopidogrel group), with a standard deviation of 0.20 for both groups. According to our previous experience the correlation coefficient between preprocedural and postprocedural cTnI is approximately 0.7. Based on previously published methods,^{28,29} we have estimated a sample size of 152 patients (38 patients for each group) to achieve a statistical power of 80% with $\alpha=0.05$, incorporating a dropout rate of 15% (pci failure, revoked consent, etc.)

Statistical analyses have been performed using IBM SPSS Statistics v21, (IBM Corporation), and Power Analysis v1.4 (A&X Analytics).

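### The one-day path for clopidogrel-pretreated patients need not be fixed and recorded before the open-label drug envelope is opened, and neither randomisation nor the primary ANCOVA accounts for pretreatment or indication

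*Combined protocol and SAP*

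**What the plan says.** All references are to the combined protocol and SAP.

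- **Two paths.** The standard course is drug randomisation on Day 1 and RIPC randomisation plus PCI on Day 2. For patients on clopidogrel for 3–7 days, 3.1 (repeated in 5.1) states that "actions performed on Day 1 and Day 2 may be combined into a single day provided that" (a) 24 hours have passed since the last clopidogrel dose when the drug is randomised, and (b) 2–4 hours separate that step, with drug intake, from the RIPC randomisation.
- **Different regimen.** The 3.1 footnotes give these patients their own regimen. In the ticagrelor arm the load falls on the procedure day and there is no second dose. In the clopidogrel arm there is no load, and the 75 mg dose is ideally given 2–3 hours before the procedure.
- **Open label.** Section 5.3 describes an open-label trial with blinded assessors.
- **Randomisation.** Section 5.1.1: "Patient randomization in the ticagrelor and the clopidogrel group will take place using sealed, opaque envelopes containing a computer-generated randomization scheme". It names no stratification factor.
- **Primary analysis.** Section 12.2 enters drug and RIPC as "fixed factors and pre-procedural cTnI as a covariate". There are no other terms.
- **Data available.** Section 6.2 records the indication (stable CAD or NSTE-ACS) and prior medication at screening. It also says that patients already on clopidogrel will have a single combined assessment, with no hint that this is optional.

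**The concern.** A patient's path and pretreatment status go with a different pre-PCI regimen and possibly a different interval from study drug to PCI. Either could plausibly relate to the 24-hour cTnI. Two separate things are at stake.

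1. **A route to bias.** The drug is open label, and nothing requires the path to be settled before the envelope is opened. If an investigator could settle it afterwards, the mix of paths could come to differ between drug arms for reasons other than chance.
2. **Precision.** Pretreatment and indication are baseline characteristics. Leaving them out of both randomisation and the model does not bias a randomised comparison. It does leave explainable variance in the error term and chance imbalance unadjusted, in a trial planned at about 80% power.

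**Working it through.** **1. The plan's own figure.** Inputs from 12.2 and 12.3: "all statistical tests will be performed tow-sided with a type I error rate of 5" per cent; "to achieve a statistical power of 80" per cent; RIPC means "0.08ng/mL for the ticagrelor group and 0.12 for the clopidogrel group"; control means "0.14ng/mL for the ticagrelor group and 0.24 for the clopidogrel group"; "with a standard deviation of 0.20 for both groups"; correlation 0.7; dropout 15%.

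- Drug main effect: (0.12 + 0.24)/2 − (0.08 + 0.14)/2 = 0.07 ng/mL.
- Residual SD: 0.20 × √(1 − 0.7²) = 0.1428; variance 0.0204.
- Per drug arm: 2 × (1.960 + 0.842)² × 0.0204 / 0.07² = 65.4, so 66; total 132.
- Dropout: 132 × 1.15 = 151.8, so 152, as stated. (132/0.85 gives 156; this does not affect the point.)
- Standard error of the drug contrast at 66 per arm: 0.1428 × √(2/66) = 0.0249. Power 80.4%.

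**2. When is the path set?** The relevant text, side by side:

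| Text | Points to |
|---|---|
| 3.1, 5.1: combining the days is permitted, not required | a choice, with no stated moment |
| 3.1, 5.1: Day 1 is chosen relative to an already scheduled PCI | choice before allocation |
| 3.1, 5.1: condition (a) is judged at drug randomisation | choice before allocation |
| 3.1, 5.1: condition (b) can be met or missed only after drug randomisation | not settled at allocation |
| 5.1: one-day patients have the second randomisation within 2–4 hours | fixed sequence once started |
| 3.1 footnotes: procedure-day drug for pretreated patients, not limited to one path | no choice |
| 3.1 schedule: treatment initiation marked on Day 1 only | differs from the footnotes if a pretreated patient takes two days |
| 6.2: one combined assessment if already on clopidogrel | no choice |

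The text leans towards a choice made before allocation, but it does not say so, and these statements do not agree on whether there is a choice at all.

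**3. Precision.** Assume a share p of 30–50% on the one-day path and a path shift s of 0.05–0.10 ng/mL, independent of pre-procedural cTnI. The share of residual variance explained is p(1 − p)s²/0.0204.

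- Low: 0.21 × 0.0025/0.0204 = 0.026.
- High: 0.25 × 0.0100/0.0204 = 0.123.

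The ratio of effect to standard error is 0.07/0.0249 = 2.82. Adjustment raises it to 2.82/√0.974 = 2.85 or 2.82/√0.877 = 3.01. Power goes from 80.4% to about 81% or 85%.

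**4. Chance imbalance if the path is fixed beforehand.** With 76 v 76 randomised, the SD of the difference in one-day share is √(2p(1 − p)/76): 7.4 points at p = 0.3 and 8.1 at p = 0.5. The probability of a difference above 10 points is 0.18 and 0.22. One SD at p = 0.5 with a 0.05 shift moves the contrast by 0.081 × 0.05 = 0.004 ng/mL, against a standard error of 0.025. The nominal 5% level already covers this.

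**5. Bias if the path were chosen after allocation (illustration only).** Bias = difference in one-day share × path shift. Power is for bias acting against the effect.

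| Share difference | Shift (ng/mL) | Bias | % of 0.07 | Type I error | Power |
|---|---|---|---|---|---|
| 10 points | 0.02 | 0.002 | 3 | 5.1% | 78% |
| 20 points | 0.05 | 0.010 | 14 | 6.9% | 67.5% |
| 30 points | 0.05 | 0.015 | 21 | 9.3% | 60% |
| 30 points | 0.10 | 0.030 | 43 | 22.6% | 36% |

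Only pretreated patients can take the one-day path, so the share difference cannot exceed the pretreated share. A 30-point gap needs at least 30% pretreated and, at that minimum, complete separation of paths by arm.

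**The case against.** A reader might infer that investigators choose the path once they know the drug, so that time from drug to PCI differs by arm. The documents do not support that. No sentence places the choice after allocation, and the scheduling text points the other way. If PCI misses its timeframe, 3.1 and 5.1 say the patient should be withdrawn; they offer no switch of path. The 3.1 footnotes put study drug on the procedure day in both arms for pretreated patients. Followed as written, they leave little room for drug-to-PCI time to differ between arms in this subgroup. Those footnotes appear to belong to the 3.1 flow chart, which is not shown in the text available here and may settle when the path is set.

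Pretreatment also precedes randomisation, so omitting it cannot by itself bias the comparison. The larger bias figures need an arm difference of 20–30 points, roughly 2.5 to 4 SDs under chance, and so presuppose the very selection that has not been shown.

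All of this stands, and it limits the point to a missing safeguard and lost precision. It does not remove the point. An implied order of events is weak protection in an open-label trial, and the passages that imply it are inconsistent about whether the path is optional.

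**Conclusion.** The point holds as a gap in the safeguards and a missed precision gain. The protocol does not require the path to be recorded before the drug envelope is opened, and neither 5.1.1 nor 12.2 accounts for pretreatment or indication. Bias is possible but not demonstrated.

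The documents give neither the share on the one-day path nor any path effect on cTnI. The range of 3–43% of the 0.07 drug effect is therefore illustration only and should not be read as an estimate. If the path is fixed before allocation, the validity of the test is unaffected. What remains is the variance that adjustment would recover: about 3–12% under a 30–50% share and a 0.05–0.10 ng/mL shift, less if pre-procedural cTnI already absorbs part of it. The case for acting is that the change is cheap and that the planned path cannot be credibly recorded once the allocation is known.

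**What to change.** - **3.1 and 5.1:** before the first envelope is opened, record on the CRF whether the patient is pretreated with clopidogrel and which path is planned. Analyse by that record even if the course later changes; the path actually taken may be affected by allocation and should not enter the model.
- **12.2:** add pretreatment (or the pre-recorded path) and indication as factors in the primary ANCOVA. Section 4 recruits both stable CAD and NSTE-ACS, while inclusion criterion 3 in 4.1 names only NSTE-ACS. If only one indication is enrolled, that term drops out.
- **5.1.1 (optional):** keep a separate envelope series by pretreatment. This improves balance only if each series is blocked, and the section does not say whether the scheme is.
- **Wording:** reconcile the optional one-day path in 3.1 and 5.1 with the 3.1 footnotes, the Day 1 treatment mark in the 3.1 schedule and the unconditional combined assessment in 6.2. No dose or timing rule needs to change for the statistical purpose.

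**Cost:** a short CRF entry, possibly a second envelope series, and two degrees of freedom. With 132 evaluable patients, a model with intercept, drug, RIPC, their interaction and the covariate leaves 132 − 5 = 127; two more factors leave 125.
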